##### **Cumulative time (weeks) in complete remission off OCS from baseline to Week 36**

Cumulative time in complete remission while off OCS will be derived for each participant over the initial 36-week treatment period. These times will then be assigned to a set of ordered categories (which will include a category for no weeks in complete remission off OCS), to be

fully defined in the SAP. An ordered logistics regression model will be fitted to these categories, assuming proportional odds.

The model will include cumulative time as the dependent variable and treatment, baseline disease severity and time of BP diagnosis as categorical covariates. The model will be used to estimate an odds ratio, with 95% CIs.

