The primary endpoint is the proportion of participants who are in complete remission while off OCS for ≥ 2 months at Week 36.

A participant will be considered in complete remission for ≥ 2 months at Week 36 if a complete remission is recorded in the disease status eCRF at the clinical assessment which is assigned to the Week 36 visit when applying the windowing rules described previously, and a complete remission is recorded at least 55 days prior to this Week 36 date, and all evaluable disease states that are recorded during the 55 days between these assessments (ie, overall 8 weeks) are complete remission.

The disease state at each visit will be recorded on the eCRF form collecting the date of assessment and the disease state. A disease state clinical assessment reported in the eCRF as “Not Evaluable” will be considered as missing. Between two consecutive non-missing disease state assessments it will be assumed that the disease state collected at the first assessment is

current until the day before the second disease state assessment, unless intercurrent events happen. The same rule will be applied for two non-consecutive non-missing disease state assessments at windowed visits if at least one missing assessment is detected between them.

A participant will be considered off OCS for ≥ 2 months at Week 36 if off OCS on the day of the clinical assessment which is assigned to the Week 36 visit when applying the windowing rules and on the 55 days (ie, overall 8 weeks) before that date. Further details on the definition of day off OCS are contained in Section [3.1.5.1](#).

A participant will be considered in complete remission while off OCS for ≥ 2 months at Week 36 if both the definitions above are met.

Note that regardless of prior OCS use, participants who have been in complete remission while off OCS for ≥ 2 months at Week 36 will be classed as responders. For example, if participants require an increase in OCS dose after previously achieving disease control but they still taper and achieve the remission criteria by Week 36, this will be counted as response in the analysis. It is considered unlikely that this situation would emerge often, but given the clinical relevance of still being able to achieve remission and that OCS use is built into the remission definition, it is considered appropriate to count this situation as response in the analysis.

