3.4 Secondary efficacy outcome variables

3.4.1 Proportion of participants in sustained complete/partial remission on minimal OCS/off OCS for at least 2 months at Week 36

A supportive responder analysis will be performed where any participants who achieve complete or partial remission while on minimal OCS or off OCS for at least 2 months at Week 36 will be defined as responders.

The same derivation rules and the same intercurrent events described for the primary analysis will be applied.

3.4.2 Cumulative time (weeks) in complete remission off OCS from baseline to Week 36

Cumulative time in complete remission while off OCS will be derived for each participant over the initial 36-week treatment period.

Cumulative time in complete remission while off OCS will be computed summing the days included in all the time intervals between each remission and the following relapse according to the below rules.

If there is no OCS usage from and inclusive of the date when complete remission is assessed until the day before the date of relapse, then cumulative time in complete remission while off OCS will be computed in weeks as:

$$(date\ of\ relapse - date\ of\ complete\ remission) / 7$$

If there is OCS usage on the date of complete remission and the complete remission is confirmed at a later assessment after the OCS usage stop date, then cumulative time in complete remission while off OCS will be computed in weeks as:

$$(date\ of\ relapse - first\ day\ off\ OCS\ after\ remission\ and\ before\ relapse) / 7$$

If the OCS usage stop date is after the last assessment of complete remission then the time will be imputed as equal to zero.

If there is OCS usage after complete remission off OCS that is before or on the day prior to the date of relapse then, the cumulative time in complete remission while off OCS will be computed in weeks as:

$$(last\ day\ off\ OCS\ after\ remission\ and\ before\ OCS\ restart - date\ of\ complete\ remission + 1) / 7$$

For participants who do not have a relapse after a complete remission, the time interval from the complete remission until the date of the BP disease state allocated to Week 36 will be considered for computing the cumulative time in the interval.

For more details about definition of days on or off OCS see Section [3.1.5.1](#).

These times will then be assigned to a set of ordered categories:

- Category Value = 0 for cumulative time = 0 days
- Category Value = 1 for $0 < \text{cumulative time} \leq 56$ days (8 weeks)

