- Category Value = 2 for $56 \text{ days (8 weeks)} < \text{cumulative time} \leq 112$ days (16 weeks)
- Category Value = 3 for $112 \text{ days (16 weeks)} < \text{cumulative time} \leq 168$ days (24 weeks)
- Category Value = 4 for cumulative time > 168 days (24 weeks)

Depending on the distribution of the data, categories might be condensed or expanded. Any such decisions will be documented prior to unblinding.

The set of intercurrent events for this estimand consists of participants who receive medications deemed to be intercurrent events as per Section [3.1.5.2](#) and participants who withdraw from the study.

Participants who receive medications deemed to be intercurrent events as per Section [3.1.5.2](#) will be considered with a relapse on the date of start of restricted medications. For restricted medications during the study missing/partial start dates are not allowed.

Participants who withdraw from the study will be considered with a relapse starting after the last available BP disease state clinical assessment.

Note that the list of intercurrent events does not include increases in OCS dose after achieving disease control, and all doses of OCS will be included in the derivation of cumulative time in complete remission while off OCS.

3.4.2.1 Cumulative time (weeks) in complete or partial remission off OCS from baseline to Week 36

Cumulative time (weeks) in complete or partial remission off OCS from baseline to Week 36 will be also computed, as additional endpoint analysed in an exploratory way.

Derivation rules and intercurrent events described in Section [3.4.2](#) for the cumulative time in complete remission while off OCS will be applied.

3.4.3 Proportion of participants off OCS by Week 36

Participants will be defined as responders if they are off OCS by Week 36. Otherwise, participants will be classified as non-responders.

A participant will be considered off OCS at Week 36 if the participant is off OCS prior to the date of the BP disease state allocated to Week 36. Further details on the definition of days off OCS are contained in Section [3.1.5.1](#).

The set of intercurrent events for this estimand consists of participants who receive medications deemed to be intercurrent events as per Section [3.1.5.2](#) and participants who withdraw from the study. The primary estimand will regard these participants as non-responders from the time such events occur up to Week 36.

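### SAP 3.4.2 has no rule that ends time in complete remission off OCS when a later visit records partial remission, so that time is credited as complete remission

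*SAP*

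**What the plan says.** The protocol (section 9.4.2.3) names the quantity plainly: "Cumulative time in complete remission while off OCS will be derived for each participant over the initial 36-week treatment period". It leaves the ordered categories to the SAP.

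SAP 3.4.2 then gives its own counting rules:

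- The total is "computed summing the days included in all the time intervals between each remission and the following relapse".
- If no relapse follows, "the time interval from the complete remission until the date of the BP disease state allocated to Week 36 will be considered".
- OCS restart has its own formula, introduced by "If there is OCS usage after complete remission off OCS that is before or on the day prior to the date of relapse". The count then ends on the last day off OCS.
- If the participant is on OCS when complete remission is first recorded, the count starts at the first day off OCS, provided that "the complete remission is confirmed at a later assessment after the OCS usage stop date". If OCS stops only after the last complete-remission assessment, the time is set to zero.
- Restricted medication counts as a relapse on its start date. A participant who withdraws "will be considered with a relapse starting after the last available BP disease state clinical assessment".

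SAP 3.2, for the primary endpoint, has a different rule for how long a recorded state lasts. Between two non-missing assessments, the first state is taken as "current until the day before the second disease state assessment, unless intercurrent events happen".

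SAP 3.4.2.1 defines an exploratory companion, time in complete or partial remission off OCS, and reuses the 3.4.2 derivation rules. SAP 4.2.8.2 analyses the categorised times with a proportional-odds model and a nominal p-value.

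**The concern.** The endpoint is named for complete remission, but the end of the interval is defined by relapse and a few other events. Partial remission off steroids is defined separately from relapse (Protocol Table 6, repeated in SAP 3.2). It describes transient new lesions that clear within a week, whereas the lesion-count criterion for relapse requires at least three new lesions in a month. A participant can therefore leave complete remission without relapsing, and 3.4.2 gives no instruction to stop counting.

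If this is programmed as written, some of the reported weeks in complete remission would not be complete remission. Misplaced participants would enter the proportional-odds model in too high a category. The contrast between 3.4.2 and its companion 3.4.2.1 would also shrink, because both would accrue the same time after the first complete remission in these histories.

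**Working it through.** The documents give no figure for this endpoint that could be reproduced, so the check applies the two rules to the same visit histories.

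**Inputs**

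- Scheduled study day = 7 × week + 1 (SAP 3.1.4 and its Table 2): Week 16 = 113, Week 20 = 141, Week 24 = 169, Week 28 = 197, Week 32 = 225, Week 36 = 253.
- Categories (SAP 3.4.2): 0 is no days; 1 is up to 56 days; 2 is over 56 to 112; 3 is over 112 to 168; 4 is over 168.
- Assumed history: off OCS from the complete-remission visit onward, complete remission at one visit, partial remission at every later visit to Week 36, no relapse, no restricted medication, no withdrawal.

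**Formulas**

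- As written (3.4.2, no relapse): Week 36 day − day of complete remission.
- State-carry (rule of 3.2): day of next assessment − day of complete remission.

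| Complete remission at | As written | Category | State-carry | Category |
|---|---|---|---|---|
| Week 16 | 253 − 113 = 140 days | 3 | 141 − 113 = 28 days | 1 |
| Week 20 | 253 − 141 = 112 days | 2 | 169 − 141 = 28 days | 1 |
| Week 24 | 253 − 169 = 84 days | 2 | 197 − 169 = 28 days | 1 |
| Week 28 | 253 − 197 = 56 days | 1 | 225 − 197 = 28 days | 1 |

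The excess is 112, 84, 56 and 28 days. The category shift is two, one, one and none. The as-written figure in each row is also what a participant in unbroken complete remission from the same visit would receive.

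The same happens when relapse comes later. With complete remission at Week 20, partial remission at Weeks 24 and 28, and relapse at Week 32, the written rule gives 225 − 141 = 84 days (category 2) and state-carry gives 28 days (category 1).

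**Does another rule already stop the count?** The OCS-restart formula does so only if OCS is taken. The confirmation and set-to-zero rules apply only when OCS is in use at the complete-remission date. They move the start of the interval or remove it, and do not end it at a later partial remission. SAP 3.4.1 expressly adopts the primary-analysis derivation rules, but 3.4.2 does not. It refers to its own rules and gives explicit formulas, so a programmer following the text would not reach the 3.2 rule.

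**Overlap with 3.4.2.1.** In these histories, complete-plus-partial remission time from the first complete remission is again 140, 112, 84 and 56 days. From that point on, the two endpoints accrue the same time.

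**The case against.** The strongest reply is that the gap is narrow and its consequence small. Most of this stands.

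- A reader might infer that the interval ends only at a recorded relapse or at Week 36. The documents do not support that. SAP 3.4.2 also ends it at OCS restart, restricted medication and withdrawal.
- A reader might infer that any non-relapse state is readily miscredited. Protocol 8.1.1.1 uses active disease only until a Table 6 state is reached, and Table 6 defines disease control and end of consolidation as points in time that come before tapering. Relapse itself is broad, since it includes extension of lesions and daily pruritus, and adding OCS after taper also counts as relapse. What remains is mainly partial remission off OCS, below the relapse threshold.
- A reader might infer that 3.4.2 and 3.4.2.1 cannot be told apart. They still differ when partial remission comes first, or when complete remission is never reached: the latter scores zero on 3.4.2 and can score above zero on 3.4.2.1.
- The histories are constructed. With visits four weeks apart the true date of change is unobserved, so 28 days is a carry-forward convention. The Week 16 row also assumes an earlier OCS stop than the target of 4 to 5 months from randomization.
- The rule is the same in both arms. If partial remission after complete remission were commoner on placebo, it would inflate placebo time and dilute the odds ratio.
- SAP 4.2.8.1 plans by-visit summaries that separate complete from partial remission, so readers would have some view of the distinction.

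None of this supplies a stopping rule. Followed exactly, 3.4.2 still gives the wrong value for the quantity it names in the histories shown.

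**Conclusion.** The point holds in this limited form. SAP 3.4.2 does not end an interval when a later evaluable visit records a non-relapse state other than complete remission, mainly partial remission off OCS, and so credits that time as complete remission. In the two central illustrations the credit is 112 days instead of 28 and 84 days instead of 28, each one category too high. These rest on assumed visit histories at scheduled days and on the SAP's own state-carry convention.

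For an individual participant this feature can only lengthen the counted time. A reader might infer from this a bias in favour of benralizumab. The documents give no frequency of the pattern by arm, so neither the size nor the direction of any effect on the odds ratio can be stated.

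The endpoint is secondary, outside the testing hierarchy and reported with a nominal p-value. The primary endpoint is unaffected, because SAP 3.2 requires every evaluable state in its 55-day window to be complete remission. This should be corrected, but it does not threaten the main conclusion.

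**What to change.** In SAP 3.4.2, end each interval on the day before the first evaluable assessment that is not complete remission, which is the 3.2 rule. End it earlier if the first day on OCS, an intercurrent event or the Week 36 assessment comes first. Start a new interval if complete remission off OCS is recorded again, and sum the intervals.

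In SAP 3.4.2.1, state the rule separately: the interval ends at the first evaluable state that is neither complete nor partial remission, with the same earlier stops.

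The cost is SAP wording and a small programming change before unblinding. Disease state is already recorded at each visit, so no new data are needed. Reported times in complete remission would be equal or shorter.

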3.1.5.2 Restricted medications

Restricted medications are detailed in the CSP Section 6.5.2 and will be selected considering a list of ATC codes that will be agreed and documented before unblinding (for the double-blind period) and final DBL (for the OLE period).

Only certain types of restricted medications used after randomisation during the double-blind period will be considered intercurrent events in the analyses, and only these cases will be handled as described in the estimand approaches detailed in Sections [4.2.6.1](#) and [4.2.6.2](#).

The restricted medications that will be considered intercurrent events include the following treatments if given to treat the participants BP, or if given for another condition but where prolonged use is deemed likely to substantially affect their BP outcomes:

- Immunosuppressive medications
- Anti-microbial agents with anti-inflammatory properties (eg. Tetracycline antibiotics, dapsone, erythromycin) – these are specific examples only, but review prior to unblinding will confirm if any others should be considered
- Topical corticosteroids
- Any marketed or investigational biologic (monoclonal or polyclonal antibody)
- Other IPs during the study or within 12 weeks after the last dose of benralizumab/placebo

In addition, for the endpoints where an increase in OCS use post disease control is considered an intercurrent event with consequence, this will only be in the case of OCS use with the aim of treating the participants BP, in a similar approach to the restricted medications described above. Short bursts of OCS use for other conditions (eg. COPD/asthma exacerbation) will not automatically trigger the estimand approach described.

A full review on concomitant medications will be performed prior to unblinding and the final list of intercurrent events will be confirmed and documented then.

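### SAP 3.4.2 miscounts time in complete remission off OCS when OCS is restarted, without a relapse, inside a remission interval

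*SAP*

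**What the plan says.** Protocol 9.4.2.3 defines the endpoint as cumulative time in complete remission while off OCS over the 36-week period. SAP 3.4.2 derives it by "summing the days included in all the time intervals between each remission and the following relapse", with a formula for each situation:

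- **No OCS in the interval:** relapse date minus remission date.
- **OCS in use on the remission date, remission confirmed after it stops:** relapse date minus the first day off OCS.
- **OCS restarted:** "If there is OCS usage after complete remission off OCS that is before or on the day prior to the date of relapse then" the time is the last day off OCS before the restart, minus the remission date, plus 1.
- **No relapse after a remission:** "the time interval from the complete remission until the date of the BP disease state allocated to Week 36 will be considered".

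The section adds: "Note that the list of intercurrent events does not include increases in OCS dose after achieving disease control". It also says that "all doses of OCS will be included in the derivation of cumulative time in complete remission while off OCS". SAP 3.1.5.2 has a provision for steroid courses given for other illnesses: "Short bursts of OCS use for other conditions (eg. COPD/asthma exacerbation) will not automatically trigger the estimand approach described". That provision is written for endpoints in which an OCS increase counts as an intercurrent event, and this endpoint is not one of them.

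The resulting time is grouped into five ordered categories (0; up to 56; up to 112; up to 168; more than 168 days). SAP 4.2.8.2 analyses them with a proportional-odds model and a nominal p-value.

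**The concern.** The restart formula has no term for days after the OCS course ends. Counting resumes only when a relapse closes the interval and a new remission opens another. A participant whose recorded state stays complete remission throughout, and who takes one short course for an unrelated illness, gets no credit from the end of that course to the relapse. By the SAP's own definitions those days qualify: 3.2 carries the disease state forward between assessments, and 3.1.5.1 classifies each day as on or off OCS.

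A second gap concerns participants who never relapse. The restart rule is worded around a relapse date, and the sentence for participants without a relapse does not mention OCS use. The SAP does not say which of the two applies.

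At stake is the category assigned to affected participants, and so the odds ratio for this endpoint. The exploratory version in SAP 3.4.2.1 (complete or partial remission) inherits the same rules.

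**Working it through.** The plan states no figure to reproduce. The check applies the rules to worked participants.

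**Inputs.** Randomization is day 1 (SAP 3.1.4), so Week 20 is day 141, Week 28 is day 197, Week 32 is day 225 and Week 36 is day 253. Category limits are from SAP 3.4.2. The OCS dates are assumed: one seven-day course on days 181-187, entered on the OCS eCRF form with dose above 0, which is what SAP 3.1.5.1 counts. Complete remission off OCS is recorded on day 141 and at every later visit until any relapse.

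**Case A: relapse on day 225.** The restart formula plainly applies.

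- SAP rule: 180 - 141 + 1 = 40 days, category 1.
- Days in complete remission and off OCS: days 141-180 (40) plus days 188-224 (224 - 188 + 1 = 37) = 77 days, category 2.
- Shortfall: 77 - 40 = 37 days and one category.

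**Case B: no relapse, Week 36 disease state on day 253.**

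- Reading 1, restart formula with Week 36 in place of the relapse date: 180 - 141 + 1 = 40 days, category 1.
- Reading 2, the no-relapse sentence alone: 253 - 141 = 112 days, category 2. This includes 7 days on OCS.
- Days in complete remission and off OCS: days 141-180 (40) plus days 188-252 (252 - 188 + 1 = 65) = 105 days, category 2.

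Reading 1 is 65 days too low and reading 2 is 7 days too high. Only reading 1 changes the category.

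**Consistency with the primary endpoint.** SAP 3.2 requires complete remission off OCS on the Week 36 date and the 55 days before it, here days 198-253. The Case B participant stopped OCS on day 187 and was recorded in complete remission on day 197, which is 56 days before day 253, so this is a primary responder with at least 56 qualifying days. Reading 1 credits that person with 40 days in total.

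**An earlier course makes the gap larger.** With complete remission off OCS on day 113, OCS on days 127-131 and no relapse:

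- Reading 1: 126 - 113 + 1 = 14 days, category 1.
- Reading 2: 253 - 113 = 140 days, category 3.
- Day count: 140 - 5 = 135 days, category 3.

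**The case against.** Four points on the other side deserve an answer.

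1. **The no-relapse case is open to interpretation.** This stands. A reader might infer that a participant who never relapses certainly loses 65 days. The text does not support that, because the no-relapse sentence gives 112 days and the correct category. But reading 2 counts OCS days in an off-OCS endpoint, against the SAP's statement about all OCS doses. Case A does not depend on this choice.

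2. **Counting can resume.** A reader might infer that one restart ends counting permanently. It does not, since a later relapse and new remission open a new interval. The second formula also shows that the drafters provided for counting after OCS stops, but only when OCS was in use on the remission date. If stretched to Case A, that formula alone would give 225 - 188 = 37 days. Only adding it to the first 40 would give 77, and the SAP does not provide for two formulas in one interval.

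3. **The protocol defines OCS added after taper as a relapse (8.1.1.1, BP Relapse).** For restarts to treat BP this largely removes the problem. For a course given for another illness, SAP 3.4.2 does not adopt that definition, and its restart rule presupposes OCS use before any relapse. If the definition were applied in Case A, with remission recorded again on day 197, the total would be (181 - 141) + (225 - 197) = 68 days, still short of 77.

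4. **Frequency and effect are unknown.** This also stands. SAP 3.1.5.2 says how short courses are handled, not that they are expected to be common. Protocol 2.2.1 describes elderly patients with significant comorbidity, but exclusion criterion 2 removes unstable disease.

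**Conclusion.** The derivation is wrong for an OCS restart that falls inside a remission interval without a relapse. Where a relapse follows, the rule drops the qualifying days after the course: 37 of 77 in the worked case, enough to move one category. Where none follows, the SAP leaves two readings, and neither gives the correct count (40 or 112 against 105).

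This rests on the OCS being recorded on the OCS eCRF form with dose above 0 and on the disease state remaining complete remission. The dates are illustrative. The size for an individual depends on when the course falls.

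A reader might also infer that the treatment odds ratio is diluted. The documents do not establish that. They give no frequency of such courses by arm, and the two readings err in opposite directions.

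The reach is limited to a secondary endpoint with a nominal p-value outside the testing hierarchy and to the exploratory version in 3.4.2.1. No confirmatory conclusion depends on it. It should still be corrected, because the error is plain and cheap to remove.

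**What to change.** Before unblinding, replace the interval formulas in SAP 3.4.2 with a day count:

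- Cumulative time is the number of days before the Week 36 disease-state date on which the carried-forward disease state (SAP 3.2) is complete remission and the participant is off OCS (SAP 3.1.5.1), divided by 7 for weeks.
- State that counting resumes once an OCS course ends while remission continues, whether the interval ends in a relapse or at Week 36.
- Keep the rules in 3.4.2 that treat intercurrent-event medication and study withdrawal as a relapse. State whether complete remission recorded after such medication counts, since a plain day count would otherwise include it.
- Apply the same count to 3.4.2.1, with complete or partial remission as the qualifying state.

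Cases A and B can serve as programming tests, with expected results of 77 and 105 days. The cost is a short SAP revision and simpler code. Both inputs, dated disease states and OCS start and end dates, are already collected.
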